EFFECTS OF RADIO ELECTRIC ASYMMETRIC CONVEYER (REAC) NEUROBIOLOGICAL
TREATMENTS IN DIFFUSE AXONIAL INJURY: A RANDOMIZED, DOUBLE-BLIND CLINICAL
TRIAL

Unique Protocol Id: 84791824.8.0000.0068

Date: October/15/2025

Abstract

Background: Severe traumatic brain injury, particularly diffuse axonal injury (DAI), often leads to lasting neurological issues. Cerebral dysfunction in DAI can be evaluated by monitoring cerebral electrical activity (CEA) through EEG. The radio electric asymmetric conveyer (REAC) is a noninvasive method designed to rebalance cellular polarity via endogenous bioelectric fields and modulate CEA. This technique may alter CEA, which can be detected using quantitative EEG (qEEG).

Objective: To assess qEEG changes following DAI and brain wave alterations after a REAC protocol in this group.

Methods: In this prospective, randomized, double-blind clinical trial, adult (≥ 18 y.o.) DAI patients will be assigned to active or sham groups for 19 sessions of either true or sham REAC following ICU discharge. Interventions include one Neuro Postural Optimization session and 18 NPPO-BWO-G sessions (up to four per day). The main outcome is to evaluate changes in qEEG patterns through population brain electrical mapping after REAC therapies. Additionally, voluntary adults (≥ 18 y.o.) with no history of neurological diseases will be submitted to the same protocol to further comparisons between qEEG patterns.

Keywords: cognitive dysfunction; diffuse axonal injury; radio electric asymmetric conveyer; rehabilitation; traumatic brain injury.

LIST OF ACRONYMS AND ABBREVIATIONS

ANOVA.....	analysis of variance
ANP	neuropsychological assessment
BDNF.....	brain-derived neurotrophic factor
Beta-APP.....	Beta-Amyloid-Precursor-Protein
BVMT.....	Brief Visuospatial Memory Test
CE	cortical excitability
CRT	cognitive rehabilitation therapy
CONSORT	Consolidated Standards of Reporting Trials
cTBS.....	continuous theta burst stimulation
DAI.....	diffuse axonal injury
DWI	diffusion weighted imaging
EEG.....	electroencephalogram
EMP	motor evoked potential
FIC	intracortical facilitation
GABA	gamma-aminobutyric-acid
GRE.....	gradient echo
HVLT	Hopkins verbal learning test
LAT	traumatic axonal injury
LED	Light-Emitting Diode
LLLT	Low Level Light/Laser
LM	Resting Motor Threshold
LTD	Long-Term Depression
LTP.....	Long-Term Potentiation
M1.....	primary motor area

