Given the significant brain damage and multiple disabling neurological sequelae, in severe TBI patients, combined with the limited efficacy of conventional pharmacological and cognitive rehabilitation interventions, REAC may be a promising therapeutic approach for affected patients. We will conduct a randomized clinical trial to assess REAC's effects in patients with DAI.

GOALS

Primary Endpoint

- To evaluate the qEEG changes in patients with subacute/chronic DAI, following REAC neuromodulation.

Secondary Endpoint

- To evaluate the qEEG changes in adults free of neurological conditions, following REAC neuromodulation.
- To evaluate cognitive and humor changes in adults free of neurological conditions, following REAC neuromodulation.

LITERATURE REVIEW

TBI Classifications

TBI is typically a heterogeneous condition being classified by clinical severity, mechanism of injury and pathophysiology, all of which are relevant to properly determine treatment and prognosis.

From a clinical point of view, TBI is classified as mild, moderate and severe depending on the duration of the loss of consciousness, level of consciousness on the Glasgow Coma scale and the presence or absence of post-traumatic amnesia, as well as its duration. However, knowledge of other information, such as history of exogenous intoxication, use of sedatives and neuromuscular blockers, as well as orotracheal intubation, is essential to avoid misclassification of TBI [41, 42].

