The participants will be recruited when hospitalized at the Neurotraumatology Clinic of the Hospital das Clínicas Complex of the Medical School of the University of São Paulo (HCFMUSP). Overall admission and in-hospital records will be collected of each patient who meet the inclusion criteria. Patients will complete the minimum period of 6 months of TBI of follow-up.

In this study, REAC will be performed a single session of Neuro Postural Optimization (NPO), and 18 Neuro Psycho Physical Optimization – Brain Wave Optimization-G (NPPO-BWO-G) treatment sessions for 4 daily sessions. Each next of kin will receive written instructions with the date and time of the next sessions in order to avoid misunderstandings.

Search locations

The study will be conducted within the HCFMUSP, in São Paulo - SP, which has 2400 beds distributed among its 8 specialized institutes and 2 auxiliary hospitals (www.hc.fm.usp.br). The research locations in the various stages of the study are described in Table 6:

Table 6 - Stages of the study and the respective places where they will be carried out

Stage of the study	Location	Purpose
Patient selection	ICU - Neurotraumatology	
Electroencephalogram	ICU - Neurotraumatology	Brain waves mapping
Brain MRI	Central Institute	DAI diagnostic
REAC	ICU - Neurotraumatology	Intervention

DAI: diffuse axonal injury, ICU: intensive care unit, MRI: magnetic resonance imaging,

REAC: radio-electric asymmetric conveyer.

Study design

This is a prospective, randomized, double-blind, placebo-controlled clinical trial. According to the hypotheses of the present study, the sample size calculation was made considering an alpha error of 5% and based on other studies with similar design [135-140]. We estimate that 30 patients should complete the follow-up and be included in the statistical analyses. However, lack of adherence could be a problem. Thus, we estimate losses at 20% and calculated a final sample size of 36 participants. Subjects with no history of chronic neurological disorders will also be included and separated of DAI patients but submitted to the same protocols. After meeting the eligibility criteria, the participants will follow the steps of the study as described in Table 7.

Table 7 - The study steps

Patient selection	Medical record, radiology, participation consent
Step 1 (pre-intervention)	qEEG, TCD and brain4care up to 3 days before the start of REAC sessions
Step 2 (intervention)	NPO (single session)

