Step 3 (intervention)	NPPO-GW (18 sessions)
Step 4 (post-intervention)	qEEG up to 3 days after the end of REAC sessions

Follow-up discharge, 3m and 6m mRankin, GOSE, DASS 21

qEEG: quantitative electroencephalogram, TCD: transcranial Doppler, REAC: radio-electric asymmetric conveyer, NPO: neuro-postural optimization, NPPO-GW: gamma-waves neuro psycho physical optimization.

Randomization

A participant will select patients according to DAI criteria and obtain consent for participation with the next of kin for each eligible patient. Following, qEEG examinations will be performed. Up to three days after finishing NPPO-BWO sessions, a second acquisition of qEEG will be performed. All participants will be blinded between active and sham until the study is finished.

Participants will be randomly divided in a 1:1 ratio into two groups:

1. Active
2. *Sham*

The randomization process will be done in blocks interchanged, with the size of each block equal to four. The computerized system available in www.randomization.com will be used. For the persistence of allocation concealment, all evaluations will be performed using a database containing the group with a label "A" and "B". Consequently, all analyses were made without possible presumptions as to the allocation of the group.

Masking of Groups

In order to maintain masking in the study, the REAC device has a very similar shape, size, color, weight and emits very similar sounds. The participants and their families will not know which group the patient has been included up to the conclusion of the study. The entire process of selection, interview, neuropsychological evaluation and intervention with REAC will be similar in the groups, differing only the type of device used. The neuropsychologist responsible for the application of the neuropsychological tests will be unaware of the allocation of the intervention group.

Ethics

The project will be submitted to the Research Ethics Committee of the Hospital das Clínicas da Faculdade de Medicina da Universidade de São Paulo.

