Patients will be submitted qEEG testing before starting the REAC protocols and then after finishing the last session. For data collection, EEG examinations were performed using an international 10-20 electrode placement system. The examination will last 30 minutes, 15 minutes with eyes open and 15 minutes with eyes closed (relaxed wakefulness. The digital 19-channel Nihon Kohden® EEG 1200 version 01.71 (Nihon Kohden, Tokyo, Japan) will be used., The channels follow the 10-20 system: seven located in the frontal lobe (Fz, Fp1, Fp2, F3, F4, F7 and F8), three in the center (Cz, C3 and C4), four in the temporal lobe (T3, T4, T5 and T6), three in the parietal lobe (Pz, P3 and P4) and two in the occipital lobe (O1 and O2). For quantitative analysis, the data were converted using the Neuromap of the Neuroworkbench software, transferred to Matlab vR2002b and treated with the EEGLab v2023.0116 software. After being imported into EEGLAB, the spatial coordinates of each electrode will be inserted according to the 10-20 system. The signals were referenced using the average between the channels. The baseline was automatically removed using a 0.5Hz 117 high-pass filter. Artifacts are automatically rejected and incorrect data periods removed. Finally, the Independent Component Analysis is performed.

Processing

Using EEGLab's Darbeliai tool, the power spectral density of each channel is calculated for four bands: delta (1-4 Hz), theta (4-8 Hz), alpha (8-13 Hz), beta (13-32 Hz), in which the absolute power will be determined. The relative power analysis will be performed using the Fast Fourier Transform FFT.

OUTCOMES

Primary:

Observe if there are significant changes in the electroencephalographic pattern, compared between the groups.

Secondary:

Observe if there are:

Significant clinical improvement determined by the mRankin and GOSE scales between the groups.

Statistical analysis

Categorical variables will be presented in absolute values and relative frequencies, while continuous variables will be described in measures of central tendency and dispersion. All analyses will be performed under the intention to treat.

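### The primary outcome does not identify which EEG variable, or which single test, decides it

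*Protocol*

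**What the plan says.** The outcome is stated in three places in the protocol, always in general terms:

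- OUTCOMES, Primary: "Observe if there are significant changes in the electroencephalographic pattern, compared between the groups".
- Abstract, Methods: "The main outcome is to evaluate changes in qEEG patterns through population brain electrical mapping after REAC therapies".
- GOALS, Primary Endpoint: "To evaluate the qEEG changes in patients with subacute/chronic DAI, following REAC neuromodulation".

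The purpose line of the Quantitative Electroencephalogram procedure also speaks only of brain-wave patterns before and after the interventions. Table 7 fixes the timing: "qEEG, TCD and brain4care up to 3 days before the start of REAC sessions" at Step 1 and "qEEG up to 3 days after the end of REAC sessions" at Step 4.

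The same procedure and its Processing paragraph describe 19 channels, listed by location (7 frontal, 3 central, 4 temporal, 3 parietal, 2 occipital). They also describe four frequency bands computed on each channel, absolute and relative power, and recordings with eyes open and with eyes closed.

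In Statistical analysis, the normality check, the repeated-measures ANOVA and the within-group test are tied to neuropsychological tests or cortical excitability. The between-group Mann-Whitney test applies to delta values of an unnamed variable. A finding is significant if its p-value is below 5%.

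On masking, Randomization says that "all evaluations will be performed using a database containing the group with a label", the labels being A and B.

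**The concern.** A reader cannot tell in advance which EEG result would make the trial positive. One map-level test, four global band tests, tests by scalp region and tests by electrode all fit the wording. They carry different chances of a false-positive primary result, so the 5% in Statistical analysis does not describe the primary conclusion until one of them is chosen.

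Masking does not remove the problem. With groups labelled A and B, an analyst can compare them on every EEG value, see which differ and select among them, all before the code is broken.

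**Working it through.** **1. Is the variable named anywhere?** Setting the three statements of the outcome beside the procedure and the statistics section, the time points (Step 1 and Step 4) and the groups (active and sham) are fixed. Band, location, eye state, power measure and any map-level statistic are not. The Mann-Whitney sentence plausibly covers EEG deltas, but it does not say which delta.

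**2. How many values are open?**

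- Electrode by band: 19 × 4 = 76, for one power measure in one eye state.
- Region by band, if the five channel groups were used as regions: 5 × 4 = 20. The protocol lists these groups to describe electrode placement and does not define them as analysis regions.
- Global mean per band: 4.
- One named variable or one map-level test: 1.

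**3. Patients per arm.** Study design states: "We estimate that 30 patients should complete the follow-up and be included in the statistical analyses". At 1:1 allocation this is 15 per arm. The planned total can be reproduced as 30 × 1.2 = 36, or 18 per arm. The base of 30 cannot be checked, because no effect size, standard deviation or power is given.

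**4. Reference case: independent tests at a nominal 5%.** The chance of at least one p below 5% is 1 − 0.95^m:

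- m = 4: 18.5%
- m = 20: 64.2%
- m = 76: 98.0%, with 76 × 0.05 = 3.8 false positives expected

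EEG values are correlated, so these overstate the rate.

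**5. Correlated values.** The protocol gives no EEG correlations, so all of those below are assumptions. The simulation used normal data with no true effect and 15 per arm. Correlation was exchangeable between channels and between bands (Kronecker product). Each value was tested with the exact two-sided Mann-Whitney test on deltas, rejecting when the smaller U ≤ 64 (actual size 4.53%). There were 10,000 replicates per setting, with a Monte Carlo standard error of at most 0.5 percentage points. The table gives the chance of at least one p below 5%.

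| Values tested | Weak (channels 0.5, bands 0.2) | Middle (0.8, 0.4) | Strong (0.95, 0.8) |
|---|---|---|---|
| 1 | about 5% | about 5% | about 5% |
| 4 global bands | 16.6% | 15.4% | 11.2% |
| 20 region by band | 42.5% | 28.9% | 16.0% |
| 76 electrode by band | 86.9% | 60.4% | 26.7% |

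The single test came out at 4.3% to 4.4%, slightly below 5% because the exact test is discrete. With 18 per arm (U ≤ 99, size 4.71%) the 76-value figures are 87.4%, 60.2% and 26.9%, so arm size hardly matters here.

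**6. Does a map-level test hold the rate?** The maximum rank-sum statistic over all 76 values, referred to 399 permutations in 3,000 replicates, rejected in 5.2%, 4.4% and 4.8% of null trials at the weak, middle and strong settings.

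**7. Power of one named test.** With the exact Mann-Whitney test at 15 per arm and a normal shift, power is 71.7% for a 1.0 SD difference and 79.2% for 1.1 SD.

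**The case against.** The strongest objection is that the larger figures rest on a decision rule the protocol never states: each electrode-by-band value tested alone, with any single p below 5% counted as success. The 76 values are processing outputs, not declared endpoints, and the Abstract's reference to brain electrical mapping fits a map-level analysis at least as well. Multiplicity control is also commonly left to a statistical analysis plan. This stands. A reader might infer that 76 unadjusted tests are planned, but the protocol does not say so. What remains is narrower: the protocol does not identify its own primary variable, and its only stated criterion is p below 5% per finding.

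A reader might also infer that the false-positive rate runs from 5% to 87% purely because of the unstated choice. That mixes two sources. At a fixed correlation the choice moves the rate from about 5% to 27% (strong), 60% (middle) or 87% (weak). The differences between those three end points come from the assumed correlations.

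Two further observations may tempt a reader but do not support the point. Table 7 expands the treatment abbreviation as "NPPO-GW: gamma-waves neuro psycho physical optimization" although none of the four computed bands is called gamma, and the sample size is tied to a neuropsychological score. These are separate matters, and neither shows that the EEG outcome is undefined.

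**Conclusion.** The point holds in this form: the primary outcome does not identify the EEG variable or single test that decides it, and nothing else in the protocol narrows it. If the 5% rule is applied as written to several EEG values and any significant one counts, the primary false-positive rate exceeds 5%. In the settings examined it is at least about 11% with four global band values and at least about 27% with 76 values. These figures are illustrations, not bounds. They rest on assumed correlations, normal data, 15 per arm and the any-significant-value rule. That the variable is not named depends on none of these assumptions. It needs correcting before the EEG data are compared between groups.

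**What to change.** In OUTCOMES, before any A-versus-B comparison of the EEG data, name one primary variable. Fixing it only before unblinding is too late, because A and B can be compared while still masked. Possible wording, with the bracketed items chosen by the investigators:

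> Primary variable: change from Step 1 to Step 4 in [absolute or relative] power in [one band or band ratio], averaged over [one region or all channels], with [eyes open or eyes closed], compared once between active and sham with the Mann-Whitney test at two-sided 5%.

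The Mann-Whitney test on deltas is already in Statistical analysis. If the whole scalp map is meant, define one map-level permutation test instead and add it there. The software statement, which lists Excel and SPSS, would then also need review.

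State that all other EEG comparisons are secondary or exploratory, and that the 5% rule decides the primary conclusion only through the one named test.

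The change needs no new visits or data, but it has two costs. A true effect in another band or region becomes a secondary result. Timing may also be tight: the Chronogram gives submission in June 2024, one year of recruitment and three months of analysis, while the document is dated October 2025. The protocol does not settle how far the trial has got. If any A-versus-B comparison of the EEG data has already been made, disclose it and label the primary EEG result exploratory.

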Gennarelli *et al.* classified diffuse traumatic brain injuries into 4 groups: mild, moderate (or classical), severe concussion, and DAI [10]. DAI can also be classified as mild, moderate or severe, and mild DAI occurs in 8% of severe TBI. In this type, the coma lasts from 6 to 24 h and after the trauma and the victims may evolve with psychological or neurological deficits. The evolution is variable: 78% of the cases evolve favorably, 2% have severe sequelae, 1% evolve with persistent vegetative state (PVS) and death occurs in about 15% of the patients. Moderate DAI, present in 20% of severe TBIs, is characterized by coma for more than 24 hours and recovery is often incomplete. The evolution is favorable in 59% of the victims, with severe sequelae in 12%, PVS in 5% and fatal evolution in up to 24% of the cases. Finally, severe DAI occurs in 16% of severe TBI and is characterized by a coma lasting days or weeks. These patients have frequent signs of brainstem dysfunction and dysautonomia (systemic arterial hypertension, hyperhidrosis, and hyperthermia). The evolution is favorable in only 28% of cases; 14% have severe sequelae, 7% progress to PVS and 57% die.

Radiological Aspects

Although patients with DAI usually present exuberant clinical alterations, the abnormal findings in a considerable part of the cases are not identified by the techniques of computed tomography (CT) or conventional magnetic resonance imaging (MRI) of the brain.

Despite the limitations of conventional routine imaging techniques, some macroscopic changes may suggest the presence of DAI:

- Focal lesions of the corpus callosum, seen as hemorrhagic foci. Occasionally these hemorrhages can rupture the interventricular septum, causing ventricle hemorrhage.

- Focal lesions in the dorsolateral quadrants of the rostral portions of the brainstem. Small hemorrhagic lesions can also be seen near the superior cerebellar peduncles.
- "*Gliding Contusions*": punctate hemorrhagic lesions affecting the parasagittal white matter in the upper portion of the cerebral hemispheres, usually in the transition zone between the white and gray matter. They are often bilateral and asymmetrical.

T2/FLAIR-weighted brain MRIs (*Fluid Attenuated Inversion Recovery*), particularly in the coronal and sagittal sections, are useful in the detection of DAI involving the corpus callosum and the fornix, two areas difficult to be analyzed in routine examinations obtained in the axial plane [16].

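### DAI severity enters neither the allocation nor any named between-arm test, although the protocol's own figures make it a strong predictor of mRankin and GOSE; the cost is moderate chance imbalance and some precision, not bias

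*Protocol*

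**What the plan says.** **Prognosis by grade** (Protocol, Diffuse axonal injury, Clinical Aspects). Grade is defined by how long coma lasts, with brainstem signs frequent in the severe form.
- Mild: "mild DAI occurs in 8% of severe TBI", and "The evolution is variable: 78% of the cases evolve favorably".
- Moderate, 20% of severe TBI: "The evolution is favorable in 59% of the victims".
- Severe, 16% of severe TBI: "The evolution is favorable in only 28% of cases; 14% have severe sequelae, 7% progress to PVS and 57% die".

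**Eligibility** (Series, Tables 4 and 5). No grade is excluded. Injury must be at least one week old.

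**Allocation** (Randomization). "Participants will be randomly divided in a 1:1 ratio into two groups", in blocks of four. No stratification factor is named.

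**Outcome** (OUTCOMES, Secondary). "Significant clinical improvement determined by the mRankin and GOSE scales between the groups".

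**Tests** (Statistical analysis). Between-arm tests are Mann-Whitney on change values, a two-factor repeated-measures ANOVA tied to neuropsychological and cortical-excitability measures, and Pearson's chi-square for adverse effects. None has a severity term, and none is assigned by name to mRankin or GOSE.

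**Timing** (Study design, Table 7). mRankin and GOSE are listed at discharge, 3 months and 6 months only.

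**The concern.** The protocol reports a 50-point fall in favourable outcome from mild to severe DAI (78 minus 28), admits all three grades, and randomises only 15 to 18 patients per arm. At that size a few severe patients more in one arm can look like a treatment effect or hide one. The usual remedy for a scale outcome, a change from baseline, is not available because neither scale is scheduled before treatment. A grade recorded before randomisation is the natural substitute, and nothing in the document uses it. At stake is the precision of the clinical comparison, and its error rate in the one randomisation that is actually drawn.

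**Working it through.** **Arm sizes.** Study design plans 30 completers and 20% losses. 30 × 1.20 = 36, which reproduces the stated total (30 / 0.80 = 37.5 would give 38; this does not affect the point). At 1:1 that is 18 randomised or 15 completing per arm.

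**Grade mix (assumption).** The shares 8, 20 and 16 sum to 44, so mild 8/44 = 18%, moderate 20/44 = 45%, severe 16/44 = 36%. The enrolled mix is not stated.

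**Outcome rates.** The listed outcomes sum to 78+2+1+15 = 96, 59+12+5+24 = 100 and 28+14+7+57 = 106. Rescaled to 100%, favourable outcome is 78/96 = 0.8125, 0.590 and 28/106 = 0.264.

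**Chance imbalance.** With severe counts binomial (n per arm, probability 16/44):

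| Severe counts differ by | 18 per arm | 15 per arm |
|---|---|---|
| 3 or more | 39% | 34% |
| 5 or more | 12% | 9% |

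**Effect of an imbalance, deaths included.** Non-severe rate = (8 × 0.8125 + 20 × 0.590)/28 = 0.654. Gap to severe = 0.654 − 0.264 = 0.390. Three patients of 18: 0.390 × 3/18 = 6.5 points. Five: 0.390 × 5/18 = 10.8 points.

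**Effect of an imbalance, all deaths excluded.** Favourable rates become 78/81 = 96%, 59/76 = 78% and 28/49 = 57%. Weights 8 × 0.85 = 6.8, 20 × 0.76 = 15.2 and 16 × 0.43 = 6.88 give a severe share of 6.88/28.88 = 24%. Non-severe rate = (6.8 × 0.963 + 15.2 × 0.776)/22 = 0.834. Gap = 0.834 − 0.571 = 0.263, so three patients of 18 move the difference by 4.4 points. A difference of four or more severe patients at 18 per arm falls from 22% to 17% of trials.

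**Variance explained by grade** (between-grade variance divided by total variance of a binary favourable outcome).
- Rescaled rates: 0.0415/0.2499 = 17%.
- Rates as printed: 0.0354/0.2499 = 14%.
- Deaths excluded: 10%.

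**Imbalance against sampling error.** With the rates as printed and 18 per arm, the standard error of the difference is √(2 × 0.2499/18) = 16.7 points. Grade mix alone contributes a standard deviation of √(2 × 0.0354/18) = 6.3 points. Removing it leaves √(2 × 0.2145/18) = 15.4 points.

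**Error rate.** In 100,000 simulated null trials at 18 per arm (rates as printed), grade mix shifted the expected difference by 10 points or more in 12% of trials. In those, the unadjusted chi-square rejected 13% of the time and a grade-stratified Cochran-Mantel-Haenszel test about 5%. At 15 per arm the figures are 14% of trials, 9% and about 5%. With deaths excluded such imbalances occur in 2 to 5% of trials. Over all randomisations the unadjusted chi-square rejected in 4.5% (15 per arm) or 6.6% (18 per arm) of null trials; the 6.6% reflects the discreteness of the test at this size.

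**Power.** In ordinal simulations at 18 per arm (Mann-Whitney against rank regression with grade, assumed odds ratio 4), power rises from 39% to 43% on the full rows and from 23% to 24% with deaths excluded. Over the scenarios checked the gain is about 0 to 4 points. A large-sample approximation for an assumed 30-point difference is a little more generous, 44% to 49%.

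**The case against.** **The analysis plan may adjust.** A reader might infer that a severity imbalance will go uncorrected. The document does not support that. No test is fixed for mRankin or GOSE, the statistical analysis plan is not shown, and covariates for a secondary outcome are often left to it. What stands is that the protocol fixes an unstratified allocation, and that its own statistical section names only tests without a severity term.

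**Unstratified allocation is valid.** A reader might also infer bias. There is none on average. What remains is lost precision and a distorted error rate when the draw happens to be uneven.

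**The gradient is from another population.** The 78/59/28% figures include deaths of 15%, 24% and 57%, some of which may come before enrolment at one week or later, and the rows do not all sum to 100%. This stands, and it is why a range is given. Excluding every death goes too far the other way, since later deaths count as GOSE category 1 (Appendix). Trial patients should lie between the two cases.

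**The covariate may not be ready-made.** It is tempting to say that MRI already supplies it. It does not: the outcome gradient belongs to the coma-based clinical grade, while Table 1 grades lesions and comes with no outcome rates. Coma of at least 6 hours is used as a diagnostic threshold; nothing says that its full duration is recorded. The section TBI Classifications itself warns of misclassification under sedation and intubation. In favour of feasibility, admission and in-hospital records are collected (Recruitment and adherence strategies).

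**Impact is limited.** The outcome is secondary, and power stays low with or without adjustment. That stands too.

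**Conclusion.** The point holds as a worthwhile improvement, not as an error that invalidates the comparison. The protocol reports a strong outcome gradient by clinical DAI grade and then uses grade neither in allocation nor in any named between-arm test, with no pre-treatment mRankin or GOSE to stand in for it. Under the assumed 8:20:16 mix, a three-patient severe imbalance or worse has a probability of about 39% at 18 per arm. Three patients are worth 4.4 to 6.5 points against a standard error of about 17. Grade accounts for 10 to 17% of outcome variance, and adjustment buys 0 to 4 points of power. These figures rest on the assumed mix, a binary favourable outcome for the imbalance arithmetic, a two-sided 5% level, and the protocol's literature rates applying to the patients enrolled.

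**What to change.** - Record clinical DAI grade before randomisation, from coma duration and brainstem signs in the admission and in-hospital records, with a written rule for patients whose coma was prolonged by sedation.
- State that the between-arm analysis of GOSE and mRankin includes that grade, severe versus mild or moderate, as a covariate in a proportional-odds model or as the stratum in a stratified rank test.
- If allocation is still open, generate two block lists, one for severe and one for not severe.

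The cost is one item on the data form, a sentence or two of protocol text, a second list if it is still possible, and one or two degrees of freedom. The residual risk is misclassified grade, which would reduce the gain. Because grade is fixed before allocation, it would not introduce bias.

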The Kolmogorov-Smirnov test will be used to verify the parametric nature of the quantitative values observed in the battery of neuropsychological tests. The repeated measures related to the items neuropsychological assessment and cortical excitability will be compared through ANOVA-type analyses (*analysis of variance*) of two factors for repeated measures and the interaction test between the groups considered to test the null hypothesis[141, 142].

To compare the delta (Δ) values between the intervention groups, the Mann-Whitney test will be used. The comparison of the frequency of adverse effects according to the intervention groups will be performed using Pearson's chi-square. The Wilcoxon Rank-Sum test will be performed in the intra-group comparison regarding pre-intervention (E1) and post-early intervention (E2) performance in the neuropsychological assessment.

Statistically significant findings are those with a p-value or probability of type I error lower than 5%. The control of blinding will be done with the analysis of agreement with Cohen's kappa. The sample size is based on the TMT part B scores obtained after the intervention (E2). The analyses were performed using *Microsoft Excel* 2010 and *IBM SPSS (Statistical Package for Social Sciences)* v.21.0.

Funding

The present study will receive no funding. Device/software manufacturers will support the project providing their methods to be used in the study.

Chronogram

June 2024- Protocol submission.

Recruitment: One year.

Data analysis: Three months.

Publishing results: Manuscript submission to publication one month later.

References

1. Ghajar J. (2000) Traumatic brain injury. Lancet 356:923-929. [https://doi.org/10.1016/S0140-6736\(00\)02689-1](https://doi.org/10.1016/S0140-6736(00)02689-1)
2. Cole TB. (2004) Global road safety crisis remedy sought: 1.2 million killed, 50 million injured annually. JAMA 291:2531-2532. <https://doi.org/10.1001/jama.291.21.2531>

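### The only between-arm test of change that could apply to the qEEG primary outcome is an unadjusted Mann-Whitney on deltas; the recorded baseline is not used as a covariate and no test is expressly assigned to qEEG

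*Protocol*

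**What the plan says.** Outcomes gives the primary outcome as: "Observe if there are significant changes in the electroencephalographic pattern, compared between the groups". Table 7 schedules two recordings to serve it: "qEEG, TCD and brain4care up to 3 days before the start of REAC sessions" (Step 1) and "qEEG up to 3 days after the end of REAC sessions" (Step 4).

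Statistical analysis contains two sentences that compare arms on change:

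- For delta "values between the intervention groups, the Mann-Whitney test will be used". The variable behind the delta is not named.
- "The repeated measures related to the items neuropsychological assessment and cortical excitability will be compared through ANOVA-type analyses", with the group interaction as the test of the null hypothesis. This sentence names its outcomes, and qEEG is not among them.

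Neither sentence includes a baseline covariate, and the section does not mention qEEG. Study design plans for 30 completers at 1:1 allocation. Procedures specifies both absolute and relative band power and states no transformation.

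**The concern.** The primary question is whether EEG change differs between arms, and every patient is to have a qEEG before treatment. The only stated between-arm test that can reach that question compares raw changes.

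A change score subtracts the whole baseline value, whereas only the part that predicts follow-up is useful. When the correlation between the two recordings is moderate, the subtraction adds noise. With about 15 patients per arm, that noise costs information the trial will already have paid for, and chance baseline differences between arms are handled less well than they could be. A rank test alone also gives a p-value without an effect estimate.

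**Working it through.** **Inputs from the protocol.** 30 completers at 1:1, so 15 per arm; significance at 5% (sidedness not stated, two-sided assumed); one qEEG before and one after treatment. The stated total of 36 reproduces as 30 × 1.2 = 36. The 30 itself cannot be rebuilt, because no effect size, SD or power is given. The protocol also gives no correlation between recordings, so a range is used.

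**Step 1: variance.** Let both recordings have standard deviation S and correlation rho. Per patient:

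- change score: 2(1 − rho)S²
- ANCOVA residual: (1 − rho²)S²
- ratio: (1 − rho²) / [2(1 − rho)] = (1 + rho)/2

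| rho | Variance ratio | Standard error ratio (square root) | Completers' worth lost, 30 × (1 − ratio) |
|---|---|---|---|
| 0.3 | 0.65 | 0.81 | 10.5 |
| 0.5 | 0.75 | 0.87 | 7.5 |
| 0.7 | 0.85 | 0.92 | 4.5 |
| 0.9 | 0.95 | 0.97 | 1.5 |

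**Step 2: what the covariate alone does to power.** Assumptions, none from the protocol: band power log-normal with log-scale SD 0.7, true active/sham ratio 0.6, 15 per arm, two-sided 5%. The comparison holds the scale and the type of test fixed: a t-test on log change against ANCOVA on log power.

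| rho | t-test on log change | ANCOVA on log power |
|---|---|---|
| 0.3 | about 36% | about 51% |
| 0.5 | about 49% | about 59% |
| 0.7 | about 71% | about 76% |
| 0.8 | about 87% | about 89% |
| 0.9 | about 99% | about 99% |

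A repeat with 20,000 replicates per setting agreed to within about one percentage point.

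**Step 3: what should not be credited to the covariate.** Under the same assumptions, a Mann-Whitney on raw deltas has about 27%, 33% and 50% power at rho 0.3, 0.5 and 0.7. Setting those beside the ANCOVA figures would combine three changes: the log scale, the move from a rank test to a parametric one, and the covariate. Only the table in Step 2 isolates the covariate.

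**The case against.** **The Mann-Whitney on change is valid.** This stands. It is a conventional randomised comparison and it does use the baseline, by subtraction. Ranking also limits the pull of extreme changes. The point concerns efficiency, not validity.

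**Covariates and transformations are often left to an SAP.** This stands in part. An SAP may exist that is not at hand. But the protocol is not silent: it names an unadjusted test, so an SAP that adjusted for baseline would depart from it.

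**The gain may be small.** This stands at high correlation. At rho 0.9 nothing is gained under the assumptions used. The simulated data also follow the very model that ANCOVA assumes.

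**Stronger readings that the text does not support.**

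- A reader might infer that qEEG is tested twice, by the Mann-Whitney and by the interaction test, so that two p-values answer one question and the error rate is inflated. The protocol ties the interaction test to neuropsychological assessment and cortical excitability. The two references it cites for that method are nonparametric by title, so the exact equivalence between a two-visit interaction and a t-test on change would not carry over either.
- A reader might infer that the delta can only mean qEEG. Table 7 also repeats mRankin, GOSE and DASS 21 at discharge, 3 months and 6 months, so changes can be formed from those too. Applying the Mann-Whitney sentence to qEEG is a reasonable reading, not a stated fact.

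**Conclusion.** The point holds as a precision improvement at almost no cost, together with a gap in the text. If the delta sentence covers qEEG, the primary outcome is compared without baseline adjustment. If it does not, the protocol's statistical section gives the primary outcome no between-arm test. The same correction serves both cases.

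The variance needed falls to between 0.65 and 0.95 of the change-score variance for rho from 0.3 to 0.9, which makes standard errors about 19% to 3% smaller. In the simulated setting, power rises by about 15, 10, 5 and 2 percentage points at rho 0.3, 0.5, 0.7 and 0.8. The variance result rests on equal variances at the two recordings and a linear relation between them; the power figures also rest on the assumed SD, ratio and log-normal shape. The protocol supplies none of these, so the size is a range and not an estimate for this trial.

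**What to change.** In Statistical analysis, add a sentence that names the qEEG analysis:

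- Analyse post-treatment band power by ANCOVA, with arm as the factor and baseline power of the same measure as covariate.
- Use the log scale for absolute power, so that the effect is an active/sham ratio. For relative power, which is bounded, use a suitable scale such as the logit.
- Report the effect with its 95% CI.
- Keep the Mann-Whitney on change as a named sensitivity analysis, and state which variables the delta refers to.

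The cost is a wording change, one degree of freedom and a model assumption that the sensitivity analysis checks. No additional data or visits are needed. If an SAP exists, it should carry the same text.
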